7.5 Discontinuation of Treatment

All reasons for discontinuation of intervention must be documented in the Off Treatment Notice – Prevention Studies.

7.6 Follow-Up Period

No further follow-up will be required once the patient completes 24 weeks of study participation.

7.7 Unblinding

Patients may be unblinded to their treatment assignment on request at the end of the study, after follow-up for all patients is complete. Institutions will be notified when patient unblinding information is available for the study. For emergency unblinding criteria and procedures, see [Section 18.3](#).

8.0 TOXICITIES TO BE MONITORED AND DOSAGE MODIFICATIONS

8.1 NCI Common Terminology Criteria for Adverse Events

The CTEP Version 4.0 of the NCI Common Terminology Criteria for Adverse Events (CTCAE), will be utilized for AE reporting. The CTEP CTCAE Version 4.0 is identified and located at the CTEP website at http://ctep.cancer.gov/protocolDevelopment/electronic_applications/ctc.htm. All appropriate treatment areas should have access to a copy of the CTEP Version 4.0 of the CTCAE.

8.2 General Considerations

Patients who are taking narcotics, tramadol, gabapentin, and/or pregabalin at study registration should continue to take a stable dose of medication or should decrease their dose during study participation, as tolerated. Dose increases for these medications should be discouraged.

Patients who need additional analgesic medication during study participation are requested to take acetaminophen. Patients should not undergo therapy with other treatment modalities such as physical therapy, acupuncture, systemic steroids, or intra-articular steroid injections during study participation unless medically necessary. Usage of all medications and other therapies for treatment of pain should be documented on the **S1202** Supplemental Agents Reporting Form.

Caution should be taken if patients take aspirin or non-steroidal anti-inflammatory drugs during study participation because of the increased risk of bleeding when these medications are used in combination with duloxetine.

Caution should be taken if patients take triptan medications, tramadol, linezolid, or other serotonergic medications during study participation because of the increased risk of serotonin syndrome when these medications are used in combination with duloxetine.

Duloxetine has been associated with an increased risk of suicide. Therefore, at the day 43 and 85 study visits, the answer to question #9 on the PHQ-9 should be reviewed before the patient leaves the clinic. In addition, all patients should be asked about suicidal thoughts or actions at the Day 15 study visit and Day 99 telephone call. If a patient reports suicidal thoughts or actions, or answers anything other than "Not at all" to question #9, the treating physician should be immediately notified.

NOTE: Concomitant therapy with heparin and warfarin is not permitted while on study treatment.

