5.2 Clinical/Laboratory Criteria

- _____ a. Patients must be post-menopausal, as defined by at least one of the following:
 - 1. ≥ 12 months since the last menstrual period OR
 - 2. prior bilateral oophorectomy OR
 - 3. previous hysterectomy with one or both ovaries left in place (or previous hysterectomy in which documentation of bilateral oophorectomy is unavailable) AND (unless ≥ 60 years of age) FSH values consistent with the institutional normal values for the post menopausal state OR
 - 4. have been on LHRH agonist therapy for at least 3 months and estradiol levels drawn within 28 days prior to registration are consistent with the institutional normal values for post-menopausal state.
- _____ b. Patients must currently be taking one of the following aromatase inhibitor (AI) doses for at least 21 days prior to registration and plans to continue for at least an additional 180 days after registration. Patients may have received any number of prior AI therapies, but the first AI therapy must have started no more than 36 months prior to registration.
 - 1. anastrozole (Arimidex®) 1 mg daily
 - 2. letrozole (Femara®) 2.5 mg daily
 - 3. exemestane (Aromasin®) 25 mg daily

SWOG Patient No. _____

Patient's Initials (L, F, M) _____

- _____ c. Patients must have aromatase inhibitor (AI) associated musculoskeletal symptoms that began or increased after starting AI therapy. New musculoskeletal pain must not be due specifically to fracture or traumatic injury.
- _____ d. Patients must have completed the **S1202** Brief Pain Inventory-Short Form (BPI-SF) within 7 days prior to registration. Patients must have an "average pain" of at least 4 on the BPI-SF (item #4).
- _____ e. Patients must have Zubrod performance status of 0-2 (see [Section 10.3](#)).
- _____ f. Patients must have no known allergy or hypersensitivity to duloxetine or any of the inactive ingredients in the matching placebo.
- _____ g. Patients must not have any contraindicated concurrent illnesses listed on the duloxetine package insert including:
- Current primary psychiatric diagnosis (schizophrenia, psychosis) or suicidal ideation, history or bipolar disorder, or seizure disorder
 - History of alcohol or other substance abuse or dependence within 365 days prior to registration.
 - Chronic liver disease
 - End stage renal disease
 - Uncontrolled narrow-angle glaucoma
 - Clinically significant coagulation disorder

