7.2 Study Plan

a. Initial Visit

Before beginning the intervention, patients will have a general physical exam (including recording of weight and height) and a mandatory blood draw for whole blood and serum (see [Section 15.1](#)). The patient will complete the **S1202** Brief Pain Inventory–Short Form (BPI-SF) prior to registration to confirm eligibility (see [Section 5.2d](#)). Patients will complete the following questionnaires prior to beginning treatment with blinded study drug:

S1202 Western Ontario and McMaster Universities Osteoarthritis (WOMAC) Index (Version 3.1)

S1202 Modified-Score for the Assessment and Quantification of Chronic Rheumatoid Affections of the Hands (M-SACRAH)

S1202 FACT – ES Trial Outcome Index (Version 4)

S1202 Patient Health Questionnaire-9 (PHQ-9)

It should take the patient about 20-25 minutes to complete the questionnaires. See [Section 15.2](#) for instructions for administration of the questionnaires.

The nurse or CRA must complete the **S1202** Cover Sheet for Patient-Completed Questionnaires.

Bottle #1 and #2 are dispensed at this visit. Patients will take 1 capsule daily for the first 7 days, then increase the dose to 2 capsules daily. The dose that should be taken each day should be listed on the patient calendar (see [Section 15.2c.1](#)).

b. Follow-up Visits

Follow-up visits will occur on Day 15, 43, 85, and 169 after start of treatment. Drug adherence will be ascertained by the nurse or CRA by review of the patient completed **S1202** Intake Calendar on Day 15, 43, and 85, as well as count of blinded drug capsules on the Day 43 and 85 visits. After the Day 85 pill count, the nurse or CRA must dispense bottle #3 to the patient to complete the Day 85 to Day 91 taper. Counts of blinded drug capsules remaining should be recorded on the **S1202** Treatment Form and the patient's medical record through the Day 85 visit. Adherence to AI should be recorded on the **S1202** Treatment Form at every visit. Adverse events will be assessed and recorded on the **S1202** Adverse Event Summary Form through the Day 85 visit. Use of pain medications, steroids, physical therapy, and acupuncture will be recorded on the **S1202** Supplemental Agents Reporting Form.

The nurse or CRA will contact the patient by telephone on Day 99 to assess adverse events following study drug discontinuation. Adverse events will be recorded on the **S1202** Adverse Event Summary Form

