9.0 STUDY CALENDAR

	α		†		Π		∇		∑							
	Wk															
REQUIRED STUDIES																
	0	1	2	3	4	5	6	7	8	9	10	11	12	13	14	24
	D	D	D	D	D	D	D	D	D	D	D	D	D	D	D	D
PRE STUDY	1	8	15	22	29	36	43	50	57	64	71	78	85	92	99	169
PHYSICAL																
History *																
Physical Exam (Height, Weight and Performance Status)																
Toxicity Assessment			X				X						X			X
Drug Compliance (Intake calendar, pill count & AI adherence)			X				X						X			
Assessment of suicidality δ			X				X						X			X
LABORATORY																
FSH (if necessary)																
AST/ALT																
Total bilirubin																
Serum creatinine																
PATIENT COMPLETED QUESTIONNAIRES Σ																
S1202 BPI-SF													X			X
S1202 WOMAC		X	X										X			X
S1202 M-SACRAH		X	X										X			X
S1202 FACT-ES		X	X										X			X
S1202 Global Ratings of Change in Joint Pain and Stiffness			X										X			X
S1202 PHQ-9		X											X			

Calendar continued on next page.
Click here to see [footnotes](#).

	α		†		π		√		∫							
	Wk															
REQUIRED STUDIES	0	1	2	3	4	5	6	7	8	9	10	11	12	13	14	24
	D	D	D	D	D	D	D	D	D	D	D	D	D	D	D	D
PRE STUDY	1	8	15	22	29	36	43	50	57	64	71	78	85	92	99	169
STAFF ADMINISTERED FORMS																
S1202 Onstudy Form																
S1202 Treatment Form			X				X						X			
S1202 Supplemental Agents Reporting Form			X				X						X			X
S1202 Adverse Events Reporting Form (toxicity notation)			X				X						X			X
S1202 Cover Sheet for Patient Completed Questionnaires			X				X						X			X
S1202 Patient Treatment Satisfaction Form													X			
PROCEDURES																
Whole Blood for DNA #		X														
Blood for serum biomarkers #		X											X			
Telephone call to patient δ															X	
TREATMENT																
Dispense blinded study drug		X											X			
Duloxetine/Placebo 30mg (1 capsule) °		X											X			
Duloxetine/Placebo 60mg (2 capsules) °			X	X	X	X	X	X	X	X	X	X				

NOTE: Forms are found on the protocol abstract page on the SWOG website (www.swog.org). Forms submission guidelines may be found in [Section 14.0](#).

NOTE: Timing of the follow-up assessments are based on the start date of protocol treatment.

Click here to see [footnotes](#).

Footnotes

- α Patient reported questionnaires and blood draw must be completed prior to starting blinded drug.
- Ω On Day 15, review only the intake calendar and record AI adherence in the patient record. Do not perform pill count. See [Section 7.2b](#).

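### Section 8.2 requires the PHQ-9 suicidality item to be read at Days 43 and 85 but does not name the Initial Visit form, the only one completed before dosing

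*Combined protocol and SAP*

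**What the plan says.** Section 8.2 gives the reason for monitoring suicidality: "Duloxetine has been associated with an increased risk of suicide". It then sets two kinds of check. The first is a reading of PHQ-9 item 9, to be done while the patient is still on site: "at the day 43 and 85 study visits, the answer to question #9 on the PHQ-9 should be reviewed". The second is a direct enquiry: "all patients should be asked about suicidal thoughts or actions at the Day 15 study visit and Day 99 telephone call". The treating physician is to be told at once of any such report, or of any item-9 answer other than the lowest category. That notification sentence names no visit.

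Section 5.2g lists "Current primary psychiatric diagnosis (schizophrenia, psychosis) or suicidal ideation" among the excluded conditions. It names no instrument, questionnaire item or assessment date.

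Section 7.2a puts the PHQ-9 on the Initial Visit list: "Patients will complete the following questionnaires prior to beginning treatment with blinded study drug". A footnote to the study calendar in Section 9.0 agrees: "Patient reported questionnaires and blood draw must be completed prior to starting blinded drug". In 7.2a only the BPI-SF is tied to entry; it is completed "prior to registration to confirm eligibility". The PHQ-9 has no such link.

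**The concern.** The protocol treats item 9 as important enough to be read on the spot during treatment because of a risk it attributes to the drug. The same item is answered once before exposure, when it also bears on a stated exclusion. That administration is not on the list of forms whose item 9 must be read.

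Three things are at stake. The first is safety: a patient could disclose ideation on a trial form and start blinded drug without any protocol step having required someone to read the answer for what it says. The second is interpretation: if the baseline answer has not been read on site, a positive answer at Day 43 cannot readily be recognised there as new or pre-existing. The third is a smaller matter for the analysis set. Section 11.1 bases the primary analysis on eligible randomised patients and 13.5 does not allow registrations to be cancelled, so a disclosure recognised late could raise an eligibility question about a patient already randomised.

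The population makes a baseline reading worthwhile. Section 5.2k requires SSRIs and tricyclics to have been stopped at least 7 days before registration (28 days for fluoxetine), and objective 1.3j expects some patients to have depression at baseline.

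**Working it through.** No statistical calculation applies, and the plan gives no figure to reproduce. The check sets collection times against required reading or enquiry times.

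| Time | PHQ-9 completed? | Item-9 content review required by 8.2? | Direct suicidality question required by 8.2? |
|---|---|---|---|
| Initial Visit, before first dose | Yes (7.2a) | Not named | Not named |
| Day 15 | No | n/a | Yes |
| Day 43 | Yes (7.2b) | Yes | Not named |
| Day 85 | Yes (7.2b) | Yes | Not named |
| Day 99 call | No | n/a | Yes |

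**Coverage.** The PHQ-9 is completed 3 times and item-9 review is required at 2 of them. The one left out is the only pre-dose administration. All four times named in 8.2 fall after dosing has begun.

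**Does another section require the baseline answer to be read?**
- Sections 5.0, 5.2g and 13.4b: sites must confirm every criterion, including absence of suicidal ideation, before registration. This is a required pre-dose determination, but it is not tied to the PHQ-9.
- Section 15.2b.3: staff look over each completed questionnaire to see that every question is answered and only one answer is marked. This applies at baseline, but it checks completeness and not the meaning of an answer.
- Section 8.2, notification sentence: not limited by visit, so a positive baseline answer that someone noticed could fall under it. It does not itself require anyone to look.
- Section 14.4b: the baseline PHQ-9 is due within 7 days of registration. This is a data-submission deadline and does not bear on when site staff read the form.

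**Can the form come after registration?** Yes. Section 7.2a requires it only before the first dose, and 13.1 allows up to five working days between registration and planned start. The answer may therefore not exist when 5.2g is confirmed.

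**What is dispensed at that visit?** Bottles 1 and 2 (7.2a), which hold 7 and 154 capsules (3.1f): 7 + 154 = 161. The 7.1 schedule uses 7 × 1 = 7 capsules on Days 1-7 and 77 × 2 = 154 on Days 8-84, also 161. The patient can thus leave the Initial Visit with her supply through Day 84.

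The calendar row for suicidality assessment is not used as evidence. Its layout is broken in the available text, and pre-study marks are missing even for history and laboratory tests.

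**The case against.** The best defence is that the sections do different jobs. Section 8.2 belongs to the part on toxicity monitoring and dose modification, so its post-exposure visits fit its purpose; entry screening belongs to 5.2g. A site cannot confirm 5.2g without some determination about ideation before registration. The 15.2b.3 check puts the baseline form in front of staff, and the open-ended notification sentence could reasonably be read as applying if they see a positive answer. On this view all that is missing is a second, form-based check.

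Much of this stands. A reader might infer that no one need consider suicidality until Day 15; 5.0, 5.2g and 13.4b rule that out. A reader might also infer that 5.2g and 8.2 contradict each other. They do not: they are complementary, with a step missing between them. Nor do the documents equate a positive item-9 answer with the 5.2g exclusion, so a positive form cannot be called a proven eligibility violation.

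What remains is that an unspecified screen can miss what a patient later discloses on a form. The protocol itself relies on reading that form during treatment, and it gives no reason for omitting the pre-dose one. A completeness check does not close this, because an item can be properly completed and still go unremarked.

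**Conclusion.** The point holds as a gap in a required reading step, not as an absence of screening. No section requires the content of the Initial Visit item-9 answer to be read, and the form may be completed after eligibility has been confirmed.

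On size, up to 294 baseline forms (the planned enrolment) fall outside the 8.2 review. It would be wrong to take this as 294 patients at risk. Those affected are patients who pass 5.2g and then answer item 9 positively; the documents give no rate from which to estimate them. Sample size, power and alpha do not change. Any effect on the analysis set would come through a few late ineligibility findings, and 11.1 already allows for 8% ineligibility overall.

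The conclusion rests on the prose of 5.2g, 7.2a, 8.2 and 15.2b.3, and assumes that no separate site instruction outside these documents requires the baseline answer to be read. It is a cheap safety improvement that should be made.

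**What to change.** In 8.2, add the Initial Visit PHQ-9 to the administrations whose item 9 is reviewed while the patient is still in clinic, and state that the existing notification step applies to it. Make the study calendar agree if it does not already.

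Then reconcile 5.2g, 7.2a and 8.2 so that they say how the baseline answer relates to the eligibility determination and to the start of study drug, including the case where the form is completed after registration. What should follow a positive answer is a clinical decision for the sponsor, and none is proposed here.

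No new instrument or visit is needed. Assuming about one minute of staff time per patient, the total is 294 × 1 minute = 294 minutes, or about 4.9 hours over the whole trial. The one drawback is that reading the answer after registration may identify a few patients as ineligible once randomised. If the sponsor moved the form ahead of registration to avoid that, the change would be larger than a wording edit.

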8.3 Dose Modifications

Grade 1 and Grade 2 Toxicity

If Grade 1 or 2 toxicities occur that are felt to be possibly, probably, or definitely related to study drug, monitor as needed until problem has resolved (i.e., Grade 0), stabilized (i.e., remains as Grade 1 or Grade 2), or is otherwise explained. If Grade 1 or Grade 2 symptoms persist, the local SWOG investigator will assess whether symptom management should be initiated, or whether the dose should be reduced from 2 capsules per day to 1 capsule per day. If Grade 1 or 2 symptoms persist while taking 1 capsule per day, the local SWOG investigator will assess whether symptom management should be initiated (if that has not already been done), or whether the patient should be removed from protocol treatment. No dose re-escalations are allowed. Follow-up will be conducted at the intervals specified in the protocol.

Grade 3 or Grade 4 Toxicity

If a patient develops any Grade 3 toxicity possibly, probably, or definitely related to the study drug, the patient should decrease the dose to 1 capsule daily for 7 days (if deemed medically safe to do so). If the symptoms resolve to Grade 0-2, the dose should be continued at 1 capsule per day. This dose may be maintained if Grade 3 toxicity does not recur. If at the 1 capsule a day dose the participant is still experiencing problems, she can be given a 1 week drug holiday from the blinded study drug. Subsequently, the patient may be re-challenged at the 1 capsule per day dose. Follow-up will continue at the intervals specified in the protocol. If symptoms do not recur (i.e., if symptoms resolve to Grade 0), the dose should be maintained, and no dose re-escalations are allowed. If Grade 3 drug-related toxicity does not improve to a Grade 0, 1, or 2 level within 1 week at the reduced dose, the patient should be removed from all protocol treatment. If the patient develops any Grade 4 toxicity possibly, probably, or definitely related to the study drug, the patient should decrease the dose to 1 capsule daily for 7 days (if deemed medically safe to do so) and then be removed from protocol treatment. Patient will also be removed from protocol treatment if there is a delay of study intervention >28 days.

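### For related Grade 3 toxicity that persists after 7 days at 1 capsule, Section 8.3 both allows a holiday with re-challenge and directs removal from treatment

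*Combined protocol and SAP*

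**What the plan says.** All the relevant text is in Section 8.3, mostly in the paragraph on Grade 3 and Grade 4 toxicity. In the order in which it stands, for a related Grade 3 event:

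1. Reduction: "the patient should decrease the dose to 1 capsule daily for 7 days (if deemed medically safe to do so").
2. Continuation: "If the symptoms resolve to Grade 0-2, the dose should be continued at 1 capsule per day".
3. Maintenance: "This dose may be maintained if Grade 3 toxicity does not recur".
4. Holiday: "If at the 1 capsule a day dose the participant is still experiencing problems, she can be given a 1 week drug holiday" from blinded drug.
5. Re-challenge: "Subsequently, the patient may be re-challenged at the 1 capsule per day dose".
6. After re-challenge: "If symptoms do not recur (i.e., if symptoms resolve to Grade 0), the dose should be maintained", without re-escalation.
7. Removal: Grade 3 drug-related toxicity that "does not improve to a Grade 0, 1, or 2 level within 1 week at the reduced dose, the patient should be removed" from protocol treatment altogether.

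The paragraph on Grade 1 and 2 toxicity adds: "If Grade 1 or 2 symptoms persist while taking 1 capsule per day, the local SWOG investigator will assess whether symptom management should be initiated" (unless already started), or whether she should come off protocol treatment. It does not mention a holiday.

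**The concern.** Sentences 4 and 5 leave a patient on study and permit her to be given the drug again. Sentence 7 takes her off. If both describe the same patient at the same moment, sites working from identical text can act in opposite ways, and the patient concerned has unresolved toxicity attributed to blinded drug. That is a safety matter first. It also means that the reasons for treatment discontinuation, which Section 11.3b item 10 plans to describe, would partly reflect which sentence a site happened to follow.

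Sentences 3 and 6 raise a second question. Both make staying on 1 capsule depend on toxicity not recurring, but they define recurrence differently.

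**Working it through.** No formula applies. The check is to take each state a patient can be in and see which sentences she meets, using the numbering above.

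**After 7 days at 1 capsule**

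- *Grade 0.* Sentence 2 applies and she continues. No conflict.
- *Grade 1 or 2.* Sentence 2 applies and she continues. Sentence 7 is not triggered. Sentence 4 may offer a holiday, and the Grade 1 and 2 paragraph offers symptom management or removal at the investigator's judgement. This is a default with options, which can coexist.
- *Still Grade 3.* Sentence 2 is not met. Sentence 4 is met on its plain terms: she is on 1 capsule, she still has problems, and no grade limits the word. Sentence 7 is also met: one week at the reduced dose has passed without improvement to Grade 2 or below. Re-challenge requires her to remain on protocol treatment, and removal ends it. Both cannot be followed.

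**Can the third state be resolved from the text?** Two readings would do it.

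- *Reading 1.* The holiday is meant for lower-grade symptoms, or for Grade 3 that improved and came back. The patient still at Grade 3 is then removed. The one-week clock in sentence 7, which matches the first 7 days, supports this.
- *Reading 2.* Sentence 7 operates only after the holiday and re-challenge. The same patient may then be re-exposed. The position of sentence 7, after the re-challenge sentences, supports this.

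The two readings give opposite outcomes for one patient, and the text states neither. Section 7.4 does not settle it: it lists unacceptable toxicity without defining it, and a delay of more than 28 days, which a 1-week holiday does not reach. The text between Sections 8.3 and 8.5 is not in the available copy and could not be checked.

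**After re-challenge at 1 capsule**

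- *Grade 0.* Sentence 6 applies and the dose is maintained.
- *Grade 1 or 2.* The Grade 0 condition in sentence 6 is not met, the absence-of-Grade-3 condition in sentence 3 is met, and sentence 7 is not triggered. The Grade 1 and 2 paragraph fits her, since she is taking 1 capsule a day, but nothing in the Grade 3 paragraph points there.
- *Grade 3 again.* Sentence 7 may apply, but the paragraph does not say whether its one-week clock restarts.

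**Size.** Section 2.0 reports one Grade 3 or 4 event among 34 treated pilot patients, judged unlikely related. Excluding it leaves 0 of 34 with a related event. The patients who meet the conflict are those whose related Grade 3 toxicity also persists through a week at the reduced dose. The documents give no rate for that.

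**The case against.** The strongest reply is that the paragraph can be read harmoniously. The holiday and re-challenge are permissive, while removal is directive and tied to a grade, so the specific instruction should govern persistent Grade 3. The holiday sentence directly follows the text on patients who improved to Grade 0-2 and stayed on 1 capsule. The Grade 1 and 2 paragraph, the only other place in Section 8.3 that speaks of a problem, lets one stabilise at Grade 1 or 2. This is a fair reading, and it means that the text allows rather than orders the holiday. It does not remove the difficulty: the holiday sentence carries no grade, and an option to re-expose is still incompatible with an instruction to remove.

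Other parts of the reply stand in full and limit the point. A reader might infer any of the following, and the documents do not support them:

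- *That a patient improved to Grade 1 or 2 after the first week also faces a contradiction.* She does not; the actions open to her are compatible.
- *That Grade 1 or 2 after re-challenge has no instruction.* The Grade 1 and 2 paragraph covers it. What is missing is the cross-reference.
- *That Grade 0-2 in one sentence and Grade 0 in another contradict each other.* They stand at different steps, one while still on drug after a reduction and the other after a week off drug and re-challenge. Different thresholds may be intended. Only the two meanings of recurrence are unclear.
- *That up to about 12 duloxetine patients are at stake.* The one-sided 95% upper limit for 0 of 34 is 1 - 0.05^(1/34) = 8.4%, and 8.4% of 147 (294 split 1:1, an assumption) is about 12. That limit is for any related Grade 3 or 4 event. Grade 4 has its own unambiguous rule, and Grade 3 that improves within the week does not meet the conflict.

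**Conclusion.** The point holds for one patient state: related Grade 3 toxicity that has not improved after 7 days at 1 capsule meets two incompatible sentences, and no available section says which prevails. The differing definitions of recurrence are a secondary lack of clarity.

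The number affected cannot be derived from the documents and is probably small. That judgement rests on the pilot, which was open-label and lasted 8 weeks, and on excluding its one Grade 3 or 4 event as unlikely related.

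A reader might also infer that the primary result is compromised. The documents do not support that: Section 11.1 analyses all eligible randomized patients by intention to treat, and Sections 7.4, 9.0 and 15.2c keep questionnaires going on schedule after treatment stops. The sample size does not depend on this rule. What remains is a safety instruction that blinded sites can apply in opposite ways, and some noise in the description of why patients stopped.

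**What to change.** The sponsor and study chairs should rewrite the Grade 3 text as one ordered sequence with a single governing instruction at each step. It needs to state:

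- which grades the holiday sentence covers;
- when the removal sentence applies relative to the holiday and the re-challenge, including whether its one-week period restarts;
- what counts as recurrence after re-challenge, and which paragraph governs Grade 1 or 2 symptoms at that point, by explicit cross-reference.

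Different thresholds at different steps can stay if intended, but the text should say so. Which action is right at each step is a clinical decision for the sponsor and study chairs.

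The cost is the wording of one paragraph and its distribution to sites. The clarification itself needs no extra patients, visits or analyses.
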